8.1 Extent of Exposure

Exposure to study drug during the DBTP will be based on treatment duration, calculated as the number of days from the date of first dose of double-blind study drug to the date of last dose of double-blind study drug, inclusive. Descriptive statistics (number of patients, mean, standard deviation (SD), median, minimum, and maximum) will be presented by treatment group for the Safety Analysis Set as outlined in Table 2-2.

Patient-years during the DBTP, defined as total exposure to study drug in years, will be summarized by treatment group.

8.2 Treatment Compliance

Dosing compliance for the DBTP is defined as the number of capsules actually taken by a patient during that phase divided by the number of capsules prescribed to be taken during the DBTP multiplied by 100. The total number of capsules actually taken during the DBTP is calculated as the sum of capsules taken during the DBTP as obtained from the study drug record. The number of capsules prescribed to be taken for the DBTP is calculated by multiplying the number of days in the DBTP by the number of capsules prescribed per day.

Descriptive statistics for study drug compliance will be presented by treatment group for the entire DBTP for the Safety Analysis Set as outlined in Table 2-2.

9. EFFICACY ANALYSES

All efficacy analyses will be performed in the following analysis sets: the mITT Analysis Set, the patients with bipolar disorder with mixed features in the mITT Analysis Set, the patients with MDD with mixed feature in the mITT Analysis Set, and the bITT Analysis Set. Baseline for efficacy parameters will be defined as the last non-missing efficacy measurement prior to the first dose of double-blind study drug. All statistical hypothesis tests will be performed at the 2-sided significance level of 5% for main effects. All confidence intervals (CIs) will be 2-sided 95% CIs, unless stated otherwise.

The efficacy analyses will be performed based on the treatment to which the patient is randomized regardless of the actual treatment received.

The efficacy analyses of MADRS assessments will be based on the rater-administered MADRS.

9.1 Primary Efficacy Parameter

The primary efficacy parameter will be the change from baseline in MADRS total score at the end of Week 6 (Day 43). The MADRS contains 10 items that assess depression, with scores for each item ranging from 0 (absence of symptoms) to 6 (symptoms of maximum severity). The MADRS total score is the sum of the 10 individual items.

The primary efficacy analysis will be performed based on the mITT Analysis Set using the mixed model with repeated measures (MMRM) with terms for treatment, pooled study site, stratification variable (bipolar I, bipolar II, or MDD), visit, baseline, and treatment-by-visit and baseline-by-visit interactions. An unstructured covariance matrix will be used to model the covariance of within-patient scores. The Kenward-Roger approximation will be used to estimate denominator degrees of freedom (Kenward et al, 1997). This analysis will only use the observed post-baseline scores without imputation of missing values. The treatment difference for lumateperone 42 mg vs placebo will be estimated and reported along with the corresponding 95% CI and p-value.

In the case that the MMRM with unstructured covariance fails to converge then the Fisher scoring algorithm will be used to provide better initial values of the covariance parameters. In the rare event that model still does not converge after using those initial values, the following alternative structures will be attempted in the specified order until convergence is achieved: heterogeneous Toeplitz structure (TOEPH), heterogeneous autoregressive(1) (ARH(1)), heterogeneous compound symmetry (CSH), No Diagonal Factor Analytic (FA0(q), with q equal to the number of time points), Toeplitz structure (TOEP), autoregressive(1) (AR(1)), and compound symmetry (CS).

[figure not shown]
The primary efficacy analysis will also be performed based on subpopulation of patients associated with bipolar depression with mixed features and patients associated with MDD with mixed features in the mITT Analysis Set. The same MMRM described above will be applied to subpopulation of bipolar disorder and subpopulation of MDD without the stratification at screening as a factor.

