5.4.1 Randomization Procedures

An interactive voice response system (IVRS)/interactive web response system (IWRS) (English only) will be used to administer the randomization schedule. Unblinded biostatistics personnel not participating in the conduct of the study will generate a permuted block randomization schedule using SAS software Version 9.4 or newer for IVRS/IWRS, which will link sequential patient randomization numbers to treatment codes. In the event that the blind needs to be broken because of a medical emergency, the Investigator may unblind an individual patient's treatment allocation (Section 5.4.3). Patients will be stratified based on their Bipolar Disorder or MDD diagnosis. Also, patients with Bipolar Disorder will be further stratified by Bipolar I or Bipolar II diagnosis.

Each patient will be assigned a randomization number at the time of randomization, which will be separate from the patient identification number. Once a randomization number has been allocated to a patient, it may not be assigned to another patient.

The IVRS/IWRS will send visit notifications to the study site personnel confirming that patient data were entered. The IVRS/IWRS notifications should be filed securely at the study site.

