9.4.4 Analysis of Primary and Key Secondary Efficacy Endpoints

The study is designed to evaluate the efficacy of lumateperone 42 mg based on the following primary and key secondary efficacy endpoints:

- Primary Endpoint Change from baseline to Day 43 in the MADRS total score.
- Key Secondary Endpoint Change from baseline to Day 43 in the CGI-S score.

The treatment effect on the primary efficacy endpoint will be evaluated in the combined population of Bipolar Disorder with mixed features and MDD with mixed features using a mixed-effect model for repeated measures (MMRM) method based on the mITT Set. The model will include the change from baseline at each pre-specified time point in the MADRS total score as the response variable; treatment group (lumateperone 42 mg and placebo), visit, site (or pooled site), the stratification factor at screening (Bipolar I, Bipolar II, or MDD), and treatment group-by-visit interaction as factors; and the baseline MADRS total score and visit-by-baseline MADRS total score interaction as covariates. An unstructured covariance matrix will be used to estimate the covariance among repeated measurements within patient. In the event the convergence cannot be attained with the unstructured correlation matrix, the following alternative structures will be attempted in the specified order: heterogeneous Toeplitz structure (TOEPH), heterogeneous

autoregressive(1) (ARH(1)), heterogeneous compound symmetry (CSH), No Diagonal Factor Analytic (FA0(q), with q equal to the number of time points), Toeplitz structure (TOEP), autoregressive(1) (AR(1)), and compound symmetry (CS). Model parameters will be estimated using restricted maximum likelihood. The Kenward-Roger approximation will be used to estimate the denominator degrees of freedom.

The MMRM method described above will also be used for the primary efficacy analyses based on the subpopulation of Bipolar Disorder with mixed features in the mITT Set and based on the subpopulation of MDD with mixed features in the mITT Set.

The key secondary efficacy endpoint, change from baseline to Day 43 in the CGI-S score, will be analyzed based on the mITT Set using an MMRM method similar to the one specified for the analysis of the primary efficacy endpoint, but replacing MADRS total score with CGI-S score for the baseline and baseline-by-visit interaction terms as covariates in the model.

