The MMRM method for the key secondary efficacy endpoint will also be applied to the key secondary efficacy analyses based on the subpopulations of Bipolar Disorder with mixed features in the mITT Set and based on the MDD with mixed features in the mITT Set.

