9.2 Secondary Efficacy Parameters

[figure not shown]
The key secondary efficacy parameter will be the change from baseline to Day 43 in CGI-S score. The key secondary efficacy analysis will be performed based on the mITT Analysis Set using a MMRM similar to those for the primary efficacy parameter. The treatment difference for lumateperone 42 mg vs placebo will be estimated and reported along with the corresponding 95% CI and p-value.

The key secondary efficacy analysis will also be performed based on subpopulation of patients associated with bipolar depression with mixed features and patients associated with MDD with mixed features in the mITT Analysis Set. The same MMRM described above will be applied to the subpopulation of bipolar disorder and the subpopulation of MDD without the stratification at screening as a factor.

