14.9.2 Incomplete Stop Date

The following rules will be applied to impute the missing numeric fields for an incomplete prior or concomitant medication stop date. If the imputed stop date is before the start date (imputed or non-imputed start date), the imputed stop date will be equal to the start date.

Missing month and day

- If the year of the incomplete stop date is the same as the year of the last dose of doubleblind study drug, the month and day of the last dose of double-blind study drug will be assigned to the missing fields
- If the year of the incomplete stop date is before the year of the last dose of double-blind study drug, *December 31* will be assigned to the missing fields
- If the year of the incomplete stop date is after the year of the last dose of double-blind study drug, *January 1* will be assigned to the missing fields

Missing month only

• If only the month is missing, the day will be treated as missing and both the month and the day will be replaced according to the above procedure

Missing day only

[figure not shown]
- If the month and year of the incomplete stop date are the same as the month and year of the last dose of double-blind study drug, the day of the last dose of double-blind study drug will be assigned to the missing day
- If either the year of the incomplete stop date is before the year of the date of the last dose of double-blind study drug or if both years are the same but the month of the incomplete stop date is before the month of the date of the last dose of double-blind study drug, the last day of the month will be assigned to the missing day

• If either the year of the incomplete stop date is after the year of the date of the last dose of double-blind study drug or if both years are the same but the month of the incomplete stop date is after the month of the date of the last dose of double-blind study drug, the first day of the month will be assigned to the missing day.

15. CHANGES TO ANALYSES SPECIFIED IN THE PROTOCOL

There are no changes to the analyses specified in the protocol.

	-	

17. REFERENCES

Lu K. Sample size calculations with multiplicity adjustment for longitudinal clinical trials with missing data. Statist Med. 2012; 31:19-28.

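### The SAP drops the Bipolar I/II randomisation stratum from the bipolar subpopulation models although Protocol 9.4.4 carries it there by reference, and SAP 15 declares no change (minor)

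*SAP*

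**What the plan says.** - **Randomisation.** Protocol 5.4.1 stratifies by Bipolar Disorder or MDD and adds that "patients with Bipolar Disorder will be further stratified by Bipolar I or Bipolar II diagnosis".
- **Protocol model.** Protocol 9.4.4 lists "the stratification factor at screening (Bipolar I, Bipolar II, or MDD" among the MMRM factors. It then says: "The MMRM method described above will also be used for the primary efficacy analyses based on the subpopulation of Bipolar Disorder". The CGI-S model "will also be applied to the key secondary efficacy analyses based on the subpopulations of Bipolar Disorder" in the same way. No term is removed for either subpopulation.
- **Protocol synopsis.** The Statistical Methods entry names a two-level factor (Bipolar Disorder or MDD) and calls the subpopulation model similar to the main one.
- **SAP.** SAP 9.1 uses the three-level variable in the combined model, then applies the model to the "subpopulation of bipolar disorder and subpopulation of MDD without the stratification at screening as a factor". SAP 9.2 repeats this for CGI-S: the model "will be applied to the subpopulation of bipolar disorder and the subpopulation of MDD without the stratification at screening as a factor".
- **Declared changes.** Protocol 9 says that changes to the protocol's analysis methods will be documented in the SAP. SAP 15 says: "There are no changes to the analyses specified in the protocol".

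**The concern.** Within MDD the factor has one level, so it has to go. Within bipolar disorder two randomisation strata remain, and leaving them out is a choice for which the SAP gives no reason.

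Blocked allocation within strata balances Bipolar I and II across arms. The true variance of the treatment difference therefore contains no I/II component. A model without the stratum still counts any I/II difference as residual variance, so its standard error comes out too large.

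The bipolar test is confirmatory. Under the synopsis, the key secondary endpoint is tested only if the primary endpoint succeeds in the combined population and in both subpopulations. A reader should be able to tell which model that test uses, and at present the answer depends on the section read. The combined-population test keeps the three-level factor and is not affected.

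**Working it through.** **Inputs from the documents.** Protocol 9.1: about 87 per arm in each subpopulation, effect size 0.45, SD 9, dropout 10%, correlation 0.7, power about 80%. Allocation is 1:1 in permuted blocks.

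**Assumptions.** The documents do not give the adjusted Bipolar I-II difference D in mean change (MADRS points), the I:II split p, or the SD at earlier visits. D from 0 to 5 is tried, with splits of 80:20, 60:40 and 50:50. Baseline MADRS, pooled site and dropout over visits are not modelled here.

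**Step 1: the plan's own figure.** 174 × 0.9 = 156.6, taken as n = 156. The effect is 0.45 × 9 = 4.05 points. SE = √(4 × 81/156) = 1.441, and 4.05/1.441 = 2.81. The noncentral t gives 79.75% power at 0.05. Allowing for Hochberg across two independent subpopulations gives 78.8% (completers only) to 81.4% (MMRM information). The planned 80% is reproduced.

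**Step 2: one time point, factor omitted.** Residual variance = [81(n−3) + n·p(1−p)·D² + 81]/(n−2). For a 60:40 split and D = 4: (81 × 153 + 156 × 0.24 × 16 + 81)/154 = 84.89. The SE ratio is √(84.89/81) = 1.024. Results for 60:40:

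| D | SE inflation | Power at 0.05, omitted (kept: 79.75%) | Type I error |
|---|---|---|---|
| 0 | 0.00% | 79.75% | 5.00% |
| 1 | 0.15% | 79.67% | 4.97% |
| 2 | 0.60% | 79.42% | 4.87% |
| 4 | 2.37% | 78.41% | 4.49% |
| 5 | 3.68% | 77.64% | 4.22% |

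Across splits from 80:20 to 50:50, the power gap at 0.05 is about 0.2 to 0.35 points at D = 2, 0.9 to 1.4 at D = 4, and 1.4 to 2.2 at D = 5. At 0.025 with 60:40 it is 0.5, 1.9 and 2.9 points.

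**Step 3: what SD 9 contains.** The table treats 9 as the SD within a stratum. If 9 already includes the I/II difference, power without the factor (60:40) is 79.9%, 80.3% and 80.6% at D = 2, 4 and 5. The gap between keeping and omitting is nearly the same (0.3, 1.3 and 2.1 points), but it lies above the planned 80%.

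**Step 4: what the planned factor recovers.** The SAP 9.1 model ends with "visit, baseline, and treatment-by-visit and baseline-by-visit interactions"; stratum is a main effect with no stratum-by-visit term. The model fits one constant b over six visits: b = (1′S⁻¹d)/(1′S⁻¹1), where d is the vector of I/II differences by visit and S the covariance matrix. In large samples with complete data and 60:40, the Day 43 residual variance is 81 + 0.24(D−b)² with the factor and 81 + 0.24D² without. At D = 4:

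| Assumed pattern, correlation 0.7 | b/D | SE inflation recovered | Power recovered at 0.05 |
|---|---|---|---|
| D constant over visits | 1.000 | 100% | 1.34 points |
| D grows linearly, SD 9 throughout | 0.583 | 82% | 1.11 |
| D grows linearly, SD rises 7 to 9 | 0.228 | 40% | 0.55 |
| D grows linearly, SD rises 5 to 9 | −0.012 | −2% | −0.02 |

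**Step 5: separate simulation.** Day 43 ANCOVA, stratified blocks of 4, 174 patients, 10% random dropout, 50:50 split, and a difference of 0.5 SD (4.5 points). Type I error was 4.4% with the factor omitted and 5.1% with it kept. The mean effect was 0.450 either way, for a true 0.45.

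**The case against.** The strongest reply is that the omission is pre-specified and in plain view in SAP 9.1 and 9.2. Protocol 9 asks only that changes be documented in the SAP, without naming a section. Protocol 9.4.4 keeps the factor only by reference, and read literally it would put a one-level factor in the MDD model, so some adaptation was always implied. Under the synopsis wording the factor is constant in each subpopulation and the SAP agrees with the protocol. All of this stands. What remains is that two sections of one protocol differ, that the SAP's combined model follows 9.4.4 rather than the synopsis, and that SAP 15 neither resolves this nor gives a reason.

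Three stronger readings are tempting, and the documents support none of them:

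- *The SAP hides a departure from the protocol.* It states the omission twice, and the synopsis is consistent with it.
- *The bipolar test is biased or anti-conservative.* The estimate is unchanged and the error is on the conservative side. The condition is that dropout does not depend on a prognostic bipolar type; if it did, omitting the type would slightly weaken the missing-at-random assumption.
- *The planned 80% power is eroded.* That follows only if SD 9 is a within-stratum SD. Protocol 9.1 takes it from an earlier lumateperone bipolar depression study and does not say whether it was adjusted for bipolar type.

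The practical effect is also fairly called small. A D of 4 to 5 points would be about as large as the assumed drug effect of 4.05 points, and nothing in the documents suggests it.

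**Conclusion.** The point holds as a minor one. Measured against Protocol 9.4.4, the SAP removes a randomisation stratum from the bipolar MADRS and CGI-S models, and SAP 15 is inaccurate in reporting no change. The consequence is nil if Bipolar I and II do not differ, negligible at 1 to 2 points of difference, and at most about 2.2 power points at 0.05 over the values tried. Whether that is a loss from plan or a forgone gain above it depends on what SD 9 includes. The planned main-effect factor may recover all, part or none of it. These sizes rest on the assumed D, split, n = 156 and effect size 0.45. The firmer reason to act is that a confirmatory subpopulation test should have one unambiguous model before unblinding.

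**What to change.** In SAP 9.1 and 9.2, drop the stratification factor for the MDD subpopulation only, and keep a two-level Bipolar I/Bipolar II factor in the bipolar MMRMs for MADRS and CGI-S. Align the protocol synopsis with the three-level factor of Protocol 9.4.4. If the omission is intended, list it with a reason in SAP 15 in place of the statement that nothing changed. A stratum-by-visit term is not asked for.

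The cost is one sentence in each SAP section and a phrase in the synopsis, or one line in SAP 15. Keeping the factor uses one model degree of freedom and needs no extra patients or data, since the stratum is already recorded at randomisation.

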9.2 Secondary Efficacy Parameters

[figure not shown]
The key secondary efficacy parameter will be the change from baseline to Day 43 in CGI-S score. The key secondary efficacy analysis will be performed based on the mITT Analysis Set using a MMRM similar to those for the primary efficacy parameter. The treatment difference for lumateperone 42 mg vs placebo will be estimated and reported along with the corresponding 95% CI and p-value.

The key secondary efficacy analysis will also be performed based on subpopulation of patients associated with bipolar depression with mixed features and patients associated with MDD with mixed features in the mITT Analysis Set. The same MMRM described above will be applied to the subpopulation of bipolar disorder and the subpopulation of MDD without the stratification at screening as a factor.

9.3 Additional Efficacy Parameters

To examine the consistency of the treatment effect of lumateperone vs placebo based on the change from baseline to Day 43 in MADRS total score across demographic and baseline characteristic subgroup categories, subgroup analyses will be performed whenever applicable based on the mITT Analysis Set, the subpopulation of bipolar disorder with mixed features in the mITT Analysis Set, and the subpopulation of MDD with mixed features in the mITT Analysis Set for the following:

- Region (US; Non-US)
- Baseline disease severity (Baseline MADRS total score < 32; Baseline MADRS total score ≥ 32)
- Sex (Male; Female)
- Age group (≤ 40 years; > 40 years)
- Race group (White; Non-White)

Exploratory analysis of the primary endpoint will be performed in the subgroups of bipolar I and bipolar II of the mITT Analysis Set.

Descriptive statistics (n, mean, SD, minimum, median, and maximum) and change from baseline value of the MADRS total score and CGI-S score will be presented by treatment group at each assessment point and performed for patients randomized before Protocol Amendment 2.0 in the ITT Analysis Set.

10. SAFETY ANALYSES

The safety analysis will be performed as outlined in Table 2-2 based on the Safety Analysis Set. Safety variables will include adverse events (AE), clinical laboratory, vital signs, and ECG; suicidality as assessed by the Columbia-Suicide Severity Rating Scale (C-SSRS); manic symptoms as assessed by the Young Mania Rating Scale (YMRS); and extrapyramidal symptoms (EPS) as assessed by Abnormal Involuntary Movement Scale (AIMS), Barnes Akathisia Rating Scale (BARS), and Simpson Angus Scale (SAS) scales. For each safety parameter, the last assessment made before the first dose of double-blind study drug will be used as the baseline for all analyses of that safety parameter.

10.1 Adverse Events

[figure not shown]
AEs will be coded using the Medical Dictionary for Regulatory Activities, version 20.1 or newer.

Treatment emergent AEs (TEAE) are defined as any AEs, regardless of the relationship to study drug, that occur or worsen in severity after the first dose of study drug and on or before the date of last dose of study drug plus one day. An event that occurs is referring to an event that did not occur before, or it started 2 days or more after the end date of the previous event for the same preferred term. Severity increases is referring to an increase in severity for a continuous event during the DBTP.

The number and percentage of patients reporting TEAEs in each treatment group will be tabulated by SOC and PT; by SOC, PT, and severity; and by SOC, PT, and relationship to study drug. If more than 1 AE is coded to the same PT for the same patient, the patient will be counted only once for that PT using the most severe and most related occurrence for the summarization by severity and by relationship to study drug, respectively.

The incidence of common (\geq 5% of patients in any treatment group) TEAEs will be summarized by PT and treatment group and sorted by decreasing frequency for the lumateperone 42 mg group.

The incidence of serious adverse events (SAEs) and of AEs leading to premature discontinuation of study drug will also be summarized by SOC, PT, and treatment group and will be sorted by decreasing frequency for lumateperone 42 mg group. Listings will be presented for patients with SAEs, patients with AEs leading to premature discontinuation of study drug, patients who died (if any) and patients who died (if any) with AEs.

